Aim 3: To examine the effect of the transition from tube to oral feeding on parent stress and parent and child quality of life. Hypothesis 3A: The transition to oral feeding will temporarily increase parent stress at week 14 at the cessation of tube feeding, with a return to baseline by week 24. Hypothesis 3B: The transition to oral feeding will increase parent/child quality of life at 24 weeks compared to week 0. Children with feeding tubes have few options for treatment other than extensive inpatient stays and expensive day treatment programs. iKanEat offers an outpatient, less intensive, empirically supported effective treatment option that can improve the lives of children and families. It is imperative that we determine the efficacy and safety of the protocol including 4 weeks of megestrol before we move toward broad dissemination of the iKanEat protocol.

Aim 4: To examine the effect of the transition from tube to oral feeding on the gut microbiome. Hypothesis 4A: The transition to oral feeding will increase the variety of food consumed orally, thus diversifying the gut microbiome by week 24. Hypothesis 4B: Children who are on a blended diet formula at week 0 will have a more diverse microbiome than children on commercially prepared formula prior to transitioning to oral feeding (Week 0, 10). Little is known about the gut microbiota of children who transition from formula feeding to oral feeding. Determining the changes in the gut microbiome could add to general knowledge about how the gut microbiome adapts to changes in diet over time in children who transition from commercial or blended formulas to a diet consumed orally.

CONFIDENTIAL

This material is strictly confidential and is intended solely for the guidance of clinical investigation. Do not disclose or use except as authorized in writing by the study sponsor

3 Study Design

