3.3 Secondary Study Endpoints

Parent stress and parent and child quality of life will be the secondary study endpoints and be completed by parents at Clinic Visits at weeks 0, 10, 14, and 24.

1. Parent Stress (The Pediatric Inventory for Parents – PIP36). Parent stress will be measured via the Pediatric Inventory for Parents, a 52 item parent questionnaire developed to measure parent stress around caring for a medically complicated child. The measure has a total and four domain scale scores (communication, medical care, role function, emotional function). For the purposes of the current study, we will use only the total score. The measure has been shown to be a valid and reliable measure of pediatric illness-related parenting stress (36).
2. Child Health-Related Quality of Life (Infant Toddler Quality of Life – ITQOL47). Child quality of life in children <5 years old will be measured with the Infant Toddler Quality of Life short form questionnaire, validated for children 2 months through 5 years of age. The ITQOL has 47 items which result in 9 multi-item scales with well-established reliability (Cronbach's alpha > .70) and validity. Similar to our previous work (11), we will use the multi-item scales in our analyses.
3. Child Health-Related Quality of Life (Child Health Questionnaire Parent Form – CHQ-PF50). Child quality of life in children \geq 5 years old will be measured with Child Health Questionnaire Parent Form questionnaire. The parent-reported CHQ is normed for ages 5-to-18 and measures 14 unique physical and psychosocial concepts. The CHQ has 50 items and scores for the parent-reported versions can be analyzed at the concept level (CHQ Profile Scores) or combined to derive an overall physical and psychosocial score, (CHQ Summary Scores).
4. Parent Quality of Life (SF-36v2). Parent Quality of Life will be measured with the widely used Parent Quality of Life Short Form 36, version 2. Over 4000 studies have used the SF-36, making it a widely accepted measure, and v2 has improved reliability ($\alpha = .73-.90$), and validity (38). The 36 questions with 5 point scales have 8 scaled scores: vitality, physical functioning, bodily pain, general health perceptions, physical role functioning, emotional role functioning, social role

CONFIDENTIAL

This material is strictly confidential and is intended solely for the guidance of clinical investigation. Do not disclose or use except as authorized in writing by the study sponsor

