7.1 Sample Size Determination and Statistical Methods

For Aim1 (To assess the efficacy of megestrol as part of the 24 week iKanEat protocol), if at least 90% of the treatment group successfully transitions (in pilot 100% successfully transitioned), with 72 participants, we would have .80 power to detect an odds ratio of .21. With 60 participants, we would have power to detect an odds ratio of .18. If only 75% of the treatment group successfully transitions, we will still have .80 power to detect an odds ratio of .25 with our smallest expected sample size of 60.

For Aim 2 (To assess the safety of megestrol as part of the 24 week iKanEat protocol), all analyses are descriptive, so a power analysis is not conducted.

For Aim 3 (To examine the effect of the transition from tube to oral feeding on parent stress and parent and child quality of life), with 60 participants, we would have .78 power to detect differences in slopes over the four data points equivalent to a standardized effect size of $d=.75$ or larger. With a sample size of 72, there will be .80 power to detect a difference in slopes equivalent to a standardized effect size of .70. To answer those questions in which the grouping factor is success in treatment, such as 3A (The transition to oral feeding will temporarily increase parent stress at week 14 at the cessation of tube feeding, with a return to baseline by week 24) and 3B (The transition to oral feeding will increase parent/child quality of life at 24 weeks compared to week 0), assuming that 60% of the participants across groups are successful, we would have sufficient power to detect effects equivalent to a standardized effect size of $d=.42$ or larger. With a sample size of 60, the minimum detectable effect size would increase to $d=.59$. If 70% percent are successful, with 72 participants we can detect effects equivalent to $d=.61$, and with 60 participants $d=.70$. These are moderate sized effects.

Planned Analyses

CONFIDENTIAL

This material is strictly confidential and is intended solely for the guidance of clinical investigation. Do not disclose or use except as authorized in writing by the study sponsor

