To address Aim 3, we will model parent stress levels, child quality of life, and parent quality of life for participants in both treatment conditions over the four measurement occasions using General Linear Mixed Models. As in Aim 1, fixed effects for site will be added to the model as will sex and age at initiation. Once the shape of the trajectory over time has been modeled, a successful transition to oral feeding indicator, defined as consuming 90% or more of calories orally, will be added to the model at level 2. For 3A, the primary variable of interest will be the time by successful transition interaction on parental stress level. Estimate statements will examine group differences in stress at week 14 and 24. To address hypothesis 3B regarding Quality of Life outcomes, we will initially model the trajectory over time for each outcome with the same set of predictors as in 3A. Of primary interest will be the time by successful transition interaction on subscales for parental quality of life and the parent impact time, general health perceptions, growth and development, and parent impact emotional subscales for child quality of life which showed the greatest response to intervention in our pilot data. It is expected that some subscales such as general health perceptions and parent impact time will show more response to intervention than others. A significant positive slope for some quality of life indicators are hypothesized for those children who transition to oral feeding while stable or declining quality of life ratings are expected for those who are unable to transition to oral feeding. Finally, to complete our analyses of sex as a biological variable (SABV) we will assess study outcomes by gender.

To address Aim 4, the Shannon Index⁶⁰ will be used to determine microbial diversity. Data analysis will be completed using the paired t-test unless the data is not normally distributed in which case analysis will be completed with the Wilcoxon Signed Rank test to compare the index values of patients on each diet.

Heterogeneity of Subjects

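### Hypothesis 3A says parent stress is back at baseline by week 24, but no contrast named for stress compares week 24 with week 0

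*Combined protocol and SAP*

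**What the plan says.** Section 2 (Study Aims, Aim 3) states Hypothesis 3A: the transition "will temporarily increase parent stress at week 14 at the cessation of tube feeding, with a return to baseline by week 24". Section 7.1 repeats it in the sample size text and lists it among the questions where the grouping factor is treatment success.

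Under Planned Analyses in section 7.1, stress is modelled over four occasions (weeks 0, 10, 14 and 24) in a general linear mixed model with site, sex and age. A success indicator (at least 90% of calories by mouth) is then added. "For 3A, the primary variable of interest will be the time by successful transition interaction on parental stress level", and "Estimate statements will examine group differences in stress at week 14 and 24".

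The outcome is the Pediatric Inventory for Parents (PIP): "For the purposes of the current study, we will use only the total score" (section 3.3). The documents give no SD, no meaningful difference, no margin and no rule for deciding that stress has returned to baseline.

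**The concern.** The second half of 3A is a statement about change within families: at week 24 there is little or nothing left of the rise. That needs a comparison of week 24 with week 0 and a limit on how much residual stress counts as none. The named contrasts supply neither. They ask whether successful and unsuccessful families differ, which is another question.

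The Parent Stress paragraph in section 1.3 shows why this matters. It reports that some parents withdrew their children during the expected weight loss, and it wants to know when stress changes so that extra help can be aimed at the right time. Whether stress has gone by week 24 is a large part of that answer.

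**Working it through.** **Inputs.** From section 7.1: 60 or 72 participants, with 60% or 70% successful for Aim 3. The splits are therefore 36/24 and 42/18 at N=60, and 43/29 and 50/22 at N=72. Assumed here because the documents do not give them: two-sided .05, 80% power, effects in SD units, a 0.5-SD effect as illustration, and a week 0 to week 24 correlation r of .3, .5 or .7.

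**1. The plan's own detectable effects.** MDE = (1.960 + 0.842) × √(1/n₁ + 1/n₂).

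| Split | √(1/n₁+1/n₂) | MDE, two-sided | Stated in 7.1 |
|---|---|---|---|
| 36/24 | 0.264 | 0.74 | .59 |
| 42/18 | 0.282 | 0.79 | .70 |
| 43/29 | 0.240 | 0.67 | .42 |
| 50/22 | 0.256 | 0.72 | .61 |

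The stated figures do not reproduce. A one-sided .05 test gives 0.66, 0.70, 0.60 and 0.64, so only the .70 matches. The main point below does not depend on them.

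**2. What each contrast estimates.** Let S(t) and U(t) be mean stress at week t in families whose child did and did not transition.

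- Estimate at week 24: S(24) − U(24).
- Interaction, week 24 against week 0: [S(24) − S(0)] − [U(24) − U(0)].
- Hypothesis 3A, second half: S(24) − S(0).

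Suppose both groups start at the same level and both are still raised by δ at week 24. The first two quantities are 0 and the third is δ. The converse also fails: S can be exactly back at baseline while U is still raised, and then the first two are non-zero although 3A is true for the successful families.

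**3. Error rate in the equally raised case.** With a true difference of 0, a two-sided .05 test is non-significant with probability 1 − .05 = .95, whatever N is. More participants do not help.

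**4. Precision of the planned contrast for its own question.** Power of an unadjusted two-sample t test at d = 0.5, with noncentrality 0.5/√(1/n₁ + 1/n₂):

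| Split | Noncentrality | Power | Missed |
|---|---|---|---|
| 36/24 | 1.90 | .463 | 54% |
| 42/18 | 1.77 | .415 | 58% |
| 43/29 | 2.08 | .537 | 46% |
| 50/22 | 1.95 | .487 | 51% |

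At N=60 the 95% half-width is about 1.96 × 0.264 = 0.52 SD (36/24) to 1.96 × 0.282 = 0.55 SD (42/18). A non-significant result would therefore be compatible with sizeable differences.

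**5. The direct contrast.** For 36 families the SD of the change is √(2(1 − r)) and its standard error is that SD divided by 6. The two-sided 90% half-width is t(.95, 35) × SE, with t = 1.690. If the true change is 0, the upper limit falls below margin m with probability of about Φ(m/SE − 1.690). The table uses the noncentral t, which agrees to within about 0.01.

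| r | SE | 90% half-width | Meets 0.5 SD | Meets 0.3 SD |
|---|---|---|---|---|
| .3 | 0.197 | 0.33 | 80% | 44% |
| .5 | 0.167 | 0.28 | 90% | 55% |
| .7 | 0.129 | 0.22 | 98% | 74% |

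**The case against.** The fitted model contains what is needed. With four occasions and a success indicator it yields week 0 and week 24 means for each group, so the change can be read off the trajectory, and an estimated trajectory serves the purpose set out in section 1.3. Parent stress is also one of many secondary endpoints. All of this stands. It shows that the fix is cheap, but it does not supply the contrast or the rule: the plan names which contrasts it will look at for stress, and the one that 3A needs is not among them.

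A reader might infer two stronger things.

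- **That the trial will miss lasting parent stress more than half the time.** The miss rates in step 4 are for a difference between groups, not for stress left above baseline. They exceed one half at both N=60 splits, but are 46% and 51% at N=72. Baseline adjustment at r = .5, which the plan does not describe, would lower them to 33-46%. The standard errors implied by the plan's own detectable effects, read as 80% power and two-sided .05, give 8-48%. Nor should the 90% success rate be carried over from the Aim 1 power text, where it is the treatment group's rate; Aim 3 assumes 60% or 70% overall.
- **That the plan will report unresolved stress as resolved.** No passage says that a non-significant week 24 difference will be read as recovery. The documents are silent on interpretation.

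The 0.5-SD effect and margin are illustrations chosen here. With no PIP SD or meaningful difference in the documents, another choice changes the feasibility figures a good deal, as the 0.3-SD column shows.

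**Conclusion.** The concern holds as a mismatch between a stated hypothesis and its stated contrasts. The named stress analyses do not test week 24 against week 0, and neither a significant nor a non-significant result from them would establish a return to baseline. That conclusion rests on the text alone and needs no assumption about variance or sample size.

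The imprecision is a secondary point: 54-58% missed at N=60 and 46-51% at N=72, for a 0.5-SD group difference in an unadjusted two-sided .05 test. The documents do not support a claim that lasting stress is missed at those rates, or that it will be reported as resolved. The matter should be settled before analysis, but it concerns a secondary hypothesis and leaves the efficacy and safety conclusions on megestrol untouched.

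**What to change.** In the same mixed model, add one Estimate statement: the week 24 minus week 0 change in PIP total among families whose child transitioned, with a two-sided 90% confidence interval. Conclude that stress returned to baseline only if the upper limit is below a margin that is justified and fixed before unblinding. Otherwise report the estimate and interval and state that a return was not shown. If no margin can be justified, reword that half of 3A as descriptive and report the change with its interval.

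The rule bounds only the upper side, because the worry is stress that remains high. If two-sided equivalence is wanted, the chance of success with 36 families and a true change of zero is lower: about 63%, 83% and 97% for a 0.5-SD margin, and 0%, 12% and 50% for a 0.3-SD margin, at r = .3, .5 and .7 (normal approximation).

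The cost is SAP wording and one line of code on data already collected. The downside is that a margin has to be chosen and defended, and the claim of a return becomes harder to make.

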8. Impact of Event Scale – Revised (IES-R). The IES-R is a 22-item self-report measure (for DSM-IV) that assesses subjective distress caused by traumatic events. It is a revised version of the older version, the 15-item IES (Horowitz, Wilner, & Alvarez, 1979). The IES-R contains seven additional items related to the hyperarousal symptoms of PTSD, which were not included in the original IES. Items correspond directly to 14 of the 17 DSM-IV symptoms of PTSD. Respondents are asked to identify a specific stressful life event and then indicate how much they were distressed or bothered during the past seven days by each "difficulty" listed.
9. Demographics. Families will complete a demographic questionnaire regarding age, race, ethnicity, income, free/reduced lunch status, and parental education, along with a medical history questionnaire asking about diagnoses at birth and diagnoses at week 0. These variables will be used to describe our sample and in any covariate analyses
10. Gut microbiota. Stool will be collected at each of the 4 clinic visits (Weeks 0, 10, 14 and 24). Once participants are consented, they will be provided with a toilet hat and sterile cup for stool collection. Once collected, stool will be stored in the sterile collection cup in the participant's freezer, until it is transferred or shipped on ice to a -80° C freezer at the study site. Each sample will be labeled with less than 8 characters and each label which matches the participant ID and will start with a letter (labels may not start with a number; per Novogene guidelines). Micro tubes will be shipped on dry ice to Novogene, where samples will undergo 16s rDNA sequencing utilizing HiSeq PE250. Sequencing will occur in the V4 region with primer 515F and 806R. Data output will be 100,000 raw reads per sample.
11. Clinical care measures. Height, weight, and vital signs will be obtained at clinic visits 1-4. These measures are routine clinical care, but will the data will be used for research purposes.

CONFIDENTIAL

This material is strictly confidential and is intended solely for the guidance of clinical investigation. Do not disclose or use except as authorized in writing by the study sponsor

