12. Tube Feeding Parent Report. Some participants may receive tube feedings after the protocol dictates that they should be fully weaned due to an unsuccessful tube feeding wean or an acute illness where the child needs to temporarily resume tube feedings. Caregivers who are giving tube feedings after the weaning phase of the protocol at Week 12 will be asked to self-report the amount of tube feeding their child is receiving. The survey is four questions and asks parents to report the volume of formula given, the approximate % of total calories from tube feedings, and the reason tube feedings were given. The survey will be sent to parents daily while the participant is receiving tube feedings. Once the participant is no longer receiving tube feedings, they will not be asked to complete the survey.

Post-Intervention Survey and Qualitative Interview. The study team will conduct an online survey and qualitative interviews over the phone with parents of children who have completed the intervention. Parents who choose to participate will be verbally consented over the phone. The survey ask parents will also be asked to self-report their child's current height, weight, and tube feeding status. The 1-hour interview will ask parents about their experience of having a child with feeding issues, opinions regarding the iKanEat intervention, the health coaching, and the tube wean transition. Parents will be paid \$20 for completing the online survey, and up to \$80 for the phone interview. In total, parents may receive up to \$100 via an electronic Amazon gift card. De-identified structured interview audio recordings will be transcribed by a professional transcription service.

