6.2 Clinic Visit 1 (Week 0)

Participants will be given a full medical history and exam (including vital signs). Height and weight will both be taken in triplicate via calibrated equipment by a trained staff member. Participants taking inhaled or internasal steroids will complete a blood draw (morning cortisol). Participants who are not taking inhaled or intranasal steroids will not complete a blood draw during the Week 0 visit. If an abnormal morning cortisol value is measured, follow the redraw procedures under section 3.4 Primary Safety Endpoints. Participants will bring in a frozen stool sample. Subjects will remain on their current G or G/J tube feeding regimen as determined by their clinical feeding team. If patient is volume sensitive, the feeding team may intervene clinically by placing the subject on continuous feeds when indicated. Families will be encouraged to contact team members with questions or concerns at any time throughout the study period. Participants who complete the measures at pre-screening and complete Clinic Visit 1 will be randomized to an intervention by the study statistician. Participants will be asked measure the child's weight using a digital home weight scale. If the family does not have a digital weight scale, one will be provided to them.

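### Aim 4 names only paired tests, but Hypothesis 4B compares different children (blended versus commercial formula), so 4B has no usable test

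*Combined protocol and SAP*

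**What the plan says.** Section 2 (Study Aims) sets two hypotheses under Aim 4.

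- **4A** concerns change over time: "The transition to oral feeding will increase the variety of food consumed orally, thus diversifying the gut microbiome by week 24".
- **4B** concerns a difference between groups: "Children who are on a blended diet formula at week 0 will have a more diverse microbiome than children on commercially prepared formula". The hypothesis places this contrast before the transition to oral feeding, at Weeks 0 and 10.

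The Aim 4 analysis is given once, under Planned Analyses in Section 7.1. Diversity is measured by the Shannon index, and then: "Data analysis will be completed using the paired t-test unless the data is not normally distributed". In that event, "analysis will be completed with the Wilcoxon Signed Rank test to compare the index values of patients on each diet".

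On feeding before weaning, Section 6.2 says: "Subjects will remain on their current G or G/J tube feeding regimen as determined by their clinical feeding team". Section 3.3 (item 10) schedules stool collection at Weeks 0, 10, 14 and 24. The sample-size text in Section 7.1 covers Aims 1 to 3 only, and the statistical entry in the Study Summary covers Aim 1 only.

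**The concern.** The paired t-test and the signed-rank test both work on differences within linked pairs. In 4B a child belongs to one diet group according to the formula used at Week 0, so no child contributes a value to both groups. The two tests named for the aim therefore do not fit one of its two hypotheses.

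What is at stake is prespecification. To report 4B, the analyst would have to choose a test, and decide whether to use Week 0, Week 10, both separately or a summary of the two, with the data already in hand. Any 4B result, positive or negative, would then be open to the charge that the method was picked to suit it.

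**Working it through.** **Can any reading of the text supply a test for 4B?** The plan states no figure for Aim 4, so there is nothing to reproduce. The first check is a comparison of the passages.

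1. Suppose the diets in "analysis will be completed with the Wilcoxon Signed Rank test to compare the index values of patients on each diet" are blended and commercial formula. The contrast is then between different children. A paired test needs a partner for each child, and no matching scheme is described anywhere.
2. Suppose they are the tube diet and the oral diet of the same child. The tests are then valid, but they answer 4A, and 4B has no test.
3. Suppose the pairing is Week 0 with Week 10 within a child. That measures change before weaning, not the difference between diets.
4. The mixed model for Aim 3 is specified for parent stress and for child and parent quality of life. It is not extended to the Shannon index.

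No reading gives 4B a test. In practice, a paired test on unequal groups (12 and 48 were tried) does not run, because the two lists differ in length. With 30 in each group it runs, but the answer depends on the arbitrary order of the children. In one simulated dataset the unpaired p-value was 0.045, while the paired p-value over random pairings ran from 0.017 to 0.089 (2.5th to 97.5th percentile).

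**How much could 4B detect with a suitable test?** Inputs: 60 children (Section 4.3), all assumed to have usable stool samples; two-sided 5%; 80% power; equal variances; one week. The share on blended diet is not in the documents, so 10%, 25% and 40% are assumed. With *m* children on blended diet:

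- Standard error of the difference, in SD units, unpaired: √(1/*m* + 1/(60 − *m*)).
- The same after arbitrary pairing, which keeps only *m* from each group: √(2/*m*).
- Children dropped by pairing: 60 − 2*m*.
- Detectable *d* and power from the noncentral t distribution, with 58 degrees of freedom unpaired and *m* − 1 paired.

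| Blended / commercial | *d* at 80% power, unpaired | SE paired / unpaired | Ratio | Children dropped | Power at that *d*, arbitrary pairs |
|---|---|---|---|---|---|
| 6 / 54 | 1.226 | 0.577 / 0.430 | 1.34 | 48 | 41% |
| 15 / 45 | 0.849 | 0.365 / 0.298 | 1.22 | 30 | 58% |
| 24 / 36 | 0.751 | 0.289 / 0.264 | 1.10 | 12 | 70% |

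The last four columns are hypothetical, because the plan does not propose arbitrary pairing. They show only that forcing the named test onto 4B would waste data. It would not inflate type I error: the simulated rates were 5.1%, 5.0% and 4.9% (100,000 normal datasets each).

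**Sensitivity to the choice of test.** At the three *d* values above, the Welch test has power of about 67%, 78% and 80%, so with 6 versus 54 it loses noticeably. Averaging Weeks 0 and 10 works the other way. With an assumed within-child correlation of 0.5, the detectable *d* in single-week SD units is multiplied by √((1 + 0.5)/2) = 0.866, which gives 1.226 × 0.866 = 1.06 and 0.849 × 0.866 = 0.74 for the equal-variance test.

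**The case against.** The strongest objection is that the point carries little weight. Aim 4 has no power statement, the opening sentence of Section 3.3 names only parent stress and quality of life as secondary endpoints (stool is item 10 in the list below it), and 4B is an observational diet contrast with no bearing on whether megestrol works or is safe. A paired test on unequal groups fails visibly, so a silently wrong result is unlikely. All of this is fair. It limits the size of the point but does not supply a test for 4B.

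Second, the power figures rest on an assumed diet split and on an equal-variance test at one week. That is also correct. They illustrate scale, and the conclusion does not rest on them.

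Third, naming the Welch test with a rank-sum fallback still lets the data choose the test, and site terms could be poorly supported with up to 10 sites and perhaps six blended-diet children. Both cautions stand and are reflected in the fix.

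Fourth, formula type might be recoverable from the dietary recalls (Section 3.2) or the Week 0 medical history (Section 6.2). It might, but neither is said to record it, and the stated focus of the recalls is oral calories.

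Finally, Section 6.2 does not forbid a change of formula between Weeks 0 and 10. That is true, but an incidental change is not a planned crossover and gives no pairing for 4B.

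**Conclusion.** The concern holds. 4B is a comparison between independent groups, the only tests named for Aim 4 are paired, and nothing else in the protocol fills the gap. This is a mismatch between hypothesis and method, not merely missing detail.

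Its reach is narrow: one hypothesis on one listed secondary endpoint. 4A is properly served, if it is read as Week 0 against Week 24 within a child (the hypothesis says only by Week 24), and Aims 1 to 3 are unaffected. The plan should be corrected, but the trial's main conclusions do not depend on it.

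Even with a suitable test, 4B could reliably detect only large differences, of roughly 0.75 to 1.2 SD under the assumed splits, equal variances and a single week.

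**What to change.** In the Aim 4 paragraph of Section 7.1:

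- Keep the paired t-test or signed-rank test, assign it to 4A, and state the contrast as Week 0 versus Week 24 within a child.
- For 4B, name an independent-groups test: the Welch t-test, or the Wilcoxon rank-sum test if the data are not normal. Preferably fix one as the main test now, or give the rule for switching.
- Define the groups by formula type at Week 0, as the hypothesis does, and state how Weeks 0 and 10 are used, for example each child's mean of the two. If the weeks are tested separately, state how multiplicity is handled.
- Optionally, because diet is not randomised, add a linear mixed model with formula type, week and a random child intercept, plus the terms already used for Aim 3 ("fixed effects for site will be added to the model as will sex and age at initiation"). Site terms should be reconsidered if the blended group is very small.

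Also confirm that formula type at Week 0 is recorded. It is not among the demographic and medical-history items in Section 3.3, and the tube feeding survey comes too late: "Caregivers who are giving tube feedings after the weaning phase of the protocol at Week 12 will be asked to self-report".

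The cost is one or two sentences in the analysis plan and at most one case report form field. Stool at Weeks 0 and 10 is already collected.

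### Aim 4 asks for the effect of the tube-to-oral transition on the microbiome, but its only stated test is paired, with no visits, transition indicator or covariates; the Aim 3 mixed model would fit Hypothesis 4A better

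*Combined protocol and SAP*

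**What the plan says.** Section 2 states Aim 4 as "To examine the effect of the transition from tube to oral feeding on the gut microbiome". Hypothesis 4A predicts more variety in oral food, "thus diversifying the gut microbiome by week 24". Hypothesis 4B compares children on blended formula with children on commercial formula at weeks 0 and 10. Section 3.3 (item 10) schedules stool at all four clinic visits: weeks 0, 10, 14 and 24.

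The Aim 4 analysis in Section 7.1 is two sentences. The Shannon index "will be used to determine microbial diversity". Then: "Data analysis will be completed using the paired t-test unless the data is not normally distributed", in which case a signed-rank test is used "to compare the index values of patients on each diet". No visits, transition indicator, covariates or power are given.

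The paragraph just before it, for Aim 3, models four occasions with site, sex and age. It then adds an indicator for taking at least 90% of calories orally, and takes the time-by-transition interaction as the main interest.

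**The concern.** Within one section the plan answers two questions of the same form in different ways. Aim 3 treats transition status as necessary for studying the effect of transition; Aim 4 leaves it out.

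Two things follow if the paired test is run on all children.

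- The mean change mixes children who switched diet with children who stayed on, or went back to, tube feeds. The plan expects some of the latter: the Aim 3 power text works from "assuming that 60% of the participants across groups are successful", and Section 3.3 (item 12) provides a survey for unsuccessful weans. The protocol-compliant population is defined by drug exposure and protocol processing, so it does not clearly exclude them.
- A change over 24 weeks in one group of young children may reflect age and time as well as transition. A paired test cannot tell these apart.

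A single-pair test of 4A also leaves two of each child's four stools out of that test, and drops any child missing either member of the pair.

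**Working it through.** **The plan's own figure.** Aim 4 has no stated sample size, effect or power, so there is nothing to reproduce.

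**Inputs from the documents.**
- N = 60 analysed (Sections 4.3 and 7.1).
- Share who transition, p = .60 or .70 (Section 7.1, Aim 3 power text).
- A cross-check from the Aim 1 power text with 1:1 allocation, where control odds = treatment odds × odds ratio:
  - 90% and .21: 9 × .21 = 1.89, control 1.89/2.89 = .654, overall (.900 + .654)/2 = .777.
  - 90% and .18: 9 × .18 = 1.62, control 1.62/2.62 = .618, overall .759.
  - 75% and .25: 3 × .25 = .75, control .75/1.75 = .429, overall .589.

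So Aim 1 implies that 22% to 41% do not transition, against 30% to 40% in the Aim 3 scenarios.

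**Assumptions not in the documents.** Two-sided alpha .05, SD of change equal to 1 in both groups, no missing stools, noncentral t throughout.

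**Step 1: reference effect.** The standardized change giving 80% power if all 60 transition is d = .368 (d√60 = 2.85).

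**Step 2: all children pooled.** Let non-transitioners change by f × d.
- Mean change = d[p + (1 − p)f]
- SD = √(1 + p(1 − p)d²(1 − f)²)
- Noncentrality = (mean/SD) × √60

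| p | f | Mean | SD | Effect | Noncentrality | Power |
|---|---|---|---|---|---|---|
| .60 | 0 | .221 | 1.016 | .217 | 1.68 | .38 |
| .70 | 0 | .257 | 1.014 | .254 | 1.97 | .49 |
| .78 | 0 | .287 | 1.012 | .284 | 2.20 | .58 |
| .60 | ½ | .294 | 1.004 | .293 | 2.27 | .61 |
| .70 | ½ | .313 | 1.004 | .311 | 2.41 | .66 |

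With N = 72 and d reset to .335, the two zero-change results at 60% and 70% are again .38 and .49.

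**Step 3: transitioners only.** Noncentrality = d√(60p).
- p = .60: .368 × √36 = 2.21, power .57.
- p = .70: .368 × √42 = 2.38, power .64.

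These exceed the pooled test when f = 0, but fall slightly below it when f = ½ (.57 against .61, and .64 against .66).

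**Step 4: difference in change by transition status.** Noncentrality = d(1 − f)√(60p(1 − p)).
- p = .60, f = 0: .368 × √14.4 = 1.40, power .28.
- p = .70, f = 0: .368 × √12.6 = 1.31, power .25.
- f = ½ halves the noncentralities to .70 and .65, so power is lower still (about .10 and .09).

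**Step 5: stools.** 4A names week 24, and 4B names weeks 0 and 10. Across Aim 4 as a whole, only week 14 has no named use.

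**The case against.** **The pooled before-after test is inferred.** Section 7.1 names no visits. A paired comparison of values on each diet could mean only children observed on both diets, in which case nothing is diluted. This stands as a reading, but the text does not settle it. If it is what was meant, the plan must still define the diets, the visits and the children. The test would still be single-group, with age and time unseparated.

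**Zero change in non-transitioners is an extreme.** Entry requires over 80% of calories by tube (Section 4.1), and Section 6.4 then tapers tube feeds until they stop. A child just short of 90% oral at week 24 has changed diet greatly. This stands. With half the change, the loss is modest and restricting to transitioners gains nothing.

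**The failure rate may be lower.** The 30% to 40% is an Aim 3 power scenario, the 90% scenarios of Aim 1 imply 22% to 24%, and all completers in the previous trial transitioned (Section 1.3). This also stands, which is why the size is given as a range.

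**Stronger readings that a reader might infer.**
- *Half of the sequenced stools are wasted.* Not supported: the hypotheses name weeks 0, 10 and 24. Two stools are left out only within a single-pair test of 4A.
- *Most of Aim 4's power is lost.* Not supported: even the worst case above falls from .80 to .38, for 4A only, under zero change. The plan claims no power for Aim 4.
- *A transition indicator restores the power.* It does not: the contrast by transition status has less power than the diluted test.

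**Conclusion.** The point holds as a mismatch between aim and analysis. Aim 4 concerns the effect of the transition, its stated test carries no transition status, and the plan already has a better-suited model in the preceding paragraph for data it will collect anyway.

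If all children are pooled, power for 4A falls from .80 to about .38 to .49 at 60% to 70% success, or .58 at 78%, with zero change in non-transitioners. It falls to about .61 to .66 at 60% to 70% success if they change half as much. These figures rest on assumed alpha, equal SDs, complete stools and an inferred pooling. They show how far the result depends on an unstated choice; they do not predict this trial's power.

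The firmer gain from the change is attribution, since a single-group paired test cannot separate transition from age and time. The primary analysis is unaffected.

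**What to change.** For Hypothesis 4A, analyse the Shannon index with the Aim 3 mixed model: visit as a category (weeks 0, 10, 14 and 24), site, sex, age at initiation, the 90% transition indicator and its interaction with visit. This gives week 14 a use and keeps children who miss a stool.

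Fix one contrast in advance, such as week 24 against the mean of weeks 0 and 10, which 4B already treats as before transition. Report it for children who transitioned and as the difference from those who did not. Do not choose the baseline by testing whether weeks 0 and 10 differ: that makes the contrast depend on the data, and a non-significant difference does not show equality.

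State which children enter and what each diet means. 4B compares different children, so it needs its own unpaired comparison.

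The cost is wording in Section 7.1, with no new samples or sequencing. The downside is that the comparison by transition status is observational, as it already is in Aim 3, and has low power (about .25 to .28 with zero change in non-transitioners, less if they partly change diet). It should be presented as support for attribution, with an interval, and not as a powered test.
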